Barre Exercise in Parkinson's
NCT Number: NCT06203990

5/20/2025

I. SPECIFIC AIMS

The primary objectives of this study are to: 1) evaluate the feasibility and acceptability of a barre exercise intervention and 2) gather preliminary data regarding the effect of a barre exercise intervention on balance, strength, functional mobility and quality of life in individuals with mild to moderate Parkinson disease (PD). Individuals with PD (N=15) will be recruited to participate in a pilot barre exercise class led by a certified barre instructor. The intervention will include 24, 45-50 minute group classes (twice weekly for 12 weeks, excluding holidays). Pre- and post-intervention data collection will include assessments of balance, lower extremity strength, and functional mobility.

Specific Aim 1: Assess the feasibility and acceptability of a pilot barre exercise intervention for individuals with mild to moderate PD.

Hypothesis 1a: Participants will participate in the intervention, defined as 75% of participants attending and engaging in 75% of the exercise sessions.

Hypothesis 1b: Participants will complete the intervention study, defined as 75% of total recruited participants remaining enrolled for the total duration of the study.

Hypothesis 1c Participants will rate the intervention as acceptable and satisfactory, as measured by a post-intervention survey.

Specific Aim 2: Determine preliminary effects of a pilot barre exercise intervention on balance, strength, functional mobility and quality of life in individuals with mild to moderate PD.

Hypothesis 2a: Barre will improve functional balance, defined as an improved score on the Mini-BESTest.

Hypothesis 2b: Barre will improve functional lower extremity strength, defined as decreased time taken to complete the Five Times Sit to Stand assessment.

Additional functional strength assessments explored include a timed stair ascent and descent task and the Timed Up and Go test.

Hypothesis 2c: Barre will improve functional mobility, defined as an improvement in average gait speed measured in the Ten Meter Walk Test. Additional gait assessments explored include fast as possible and backwards walking in the Ten Meter Walk Test and distance covered in the Two Minute Walk Test.

Exploratory Hypothesis 2d: Barre will improve quality of life, as measured by the Parkinson's Disease Questionnaire (PDQ-39).

II. BACKGROUND AND SIGNIFICANCE

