If the participant meets the inclusion criteria following in-person screening, sensors will be placed on both feet, wrists, the sternum, and lumbar spine to record data during gait, balance, and functional strength assessments. All participants will be also be fitted with a gait belt and closely monitored by members of the research team to prevent falls.

Balance Assessment: Participants will first complete the Mini-BESTest, which is a clinically relevant balance test that is both valid and reliable for individuals with PD.²⁶ The sensors will record postural sway and gait data during the various sections of this test.

Gait Assessments: After completing the Mini-BESTest, participants will complete gait assessments. The sensors will record spatiotemporal gait variables during each walking task.

Two Minute Walk Test: This gait assessment will be used to measure walking endurance. Participants are asked to cover as much ground as possible over the course of two minutes. Following this assessment, the Borg Scale Rating of Perceived Exertion will be administered to measure exertion levels during the Two Minute Walk Test.

Ten Meter Walk Test: This gait assessment will be used to assess average gait speed. Participants will be asked to complete this test under three conditions: 1) normal forwards gait speed, 2) fast as possible gait speed, and 3) backwards walking at a normal, safe gait speed. Only the first condition, normal forwards gait speed, will be used as a primary outcome.

Functional Strength Assessments: Following the gait assessments, participants will complete the following functional strength assessments. These assessments will serve as proxy measures for lower extremity strength. The Borg Scale Rating of Perceived Exertion will again be administered following all of the functional strength assessments listed below.

Five Times Sit to Stand: Participants will be asked to start sitting with their arms folded across their chest and with their back against the chair. Participants are then asked to stand up and sit down five times as quickly as they can.

Stair Ascent and Descent: Participants will be asked to ascend and descend one flight of stairs (building's standard flight of 12 stairs) as quickly and safely as possible under close supervision by a research team member.

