Timed Up and Go (TUG): This test is administered as part of the Mini-BESTest. Participants will be asked to stand up from a chair, walk three meters at their normal, comfortable gait speed, and sit back down.

All motor assessments, including the MDS-UPDRS-III, balance, gait, and functional strength assessments will be filmed with participant consent. These video recordings will be stored in a secure online Box folder and will only be accessed by members of the research team to regrade assessments as necessary. Video records will be destroyed after all analyses and publications are complete.

Upon completion of the above motor evaluations, participants will be asked to complete three surveys. These include the Parkinson disease Questionnaire (PDQ-39), used to measure quality of life, the Activities-specific Balance Confidence Scale (ABC), and questions regarding current exercise habits.

Intervention

All participants will be assigned to the pilot barre exercise intervention. The intervention classes will occur in the Movement Disorders Research Center and consist of twice weekly, 45-50 minute group exercise classes for 12 weeks (excluding holidays). In total, participants will receive 24 classes. The barre exercise intervention will be delivered by an International Ballet Barre Fitness Association (IBBFA) certified barre instructor with a bachelor of arts (BA) in dance and extensive dance-teaching experience. Additional research team members will also be present in the classes to monitor safety and help participants when needed. The barre exercise program will combine elements of classical ballet and strength training, focusing on repetition of low impact, isometric movements. The class will begin with a short seated warm-up, move into 30 minutes of barre exercises holding on to the back of a chair as the fixed barre, continue into core exercises performed laying down on a mat, and finish with a cool down. After each class, the participants will rate how difficult the session was using a visual analog scale (VAS). This scale will be used to determine to what level the class should progress at as the weeks go on. Progression may include introduction of more challenging exercises and increased repetitions. Participants will be encouraged to modify the exercises as needed for safety.

Post-Intervention Visit Two

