 - Parkinson Disease Questionnaire (PDQ-39) – a patient-reported questionnaire that assesses PD-specific health quality of life in the past month
 - New Freezing of Gait Questionnaire (NFOG-Q) – a patient-reported questionnaire that assesses frequency, severity, and duration of freezing of gait episodes
 - Borg Rating Scale of Perceived Exertion – a 15-point scale with written descriptors designed to standardize perceived exertion across tasks and individuals

The following forms and assessments will also be collected during Pre-Intervention Visit 1:

- Montreal Cognitive Assessment (MoCA)- a valid, sensitive screening tool for mild cognitive impairment
- Demographics Form
- Medical History
- Medication List
- Current exercise habits survey
- Activities-specific Balance Confidence Scale (ABC) – a patient-reported questionnaire that assesses balance confidence while performing various activities
- MDS-UPDRS- gold standard measure of global disease severity in PD, including motor and non-motor symptoms as well as activities of daily living

IV. STATISICAL ANALYSES

Aim 1: Assess the feasibility and acceptability of a pilot barre exercise intervention for individuals with mild to moderate PD.

- Feasibility Objectives
 - Participation: 75% of participants will attend 75% of the 24 sessions.
 - Retention: 75% of recruited participants will complete the intervention and remain enrolled for the duration of the study.
- Satisfaction and Acceptability- Demonstrate that this group exercise class is acceptable, defined as a minimum average rating of > 1.5 out of 4 on the Client Satisfaction and Acceptability Questionnaire (CSQ).

Due to the preliminary nature of the study and small expected sample size, only motor trends, defined as average group change in score from pre- to post-intervention will be reported. Additionally, published MCIDs will be used to establish if the average improvement of the group reached clinical significance.

Aim 2: Determine the effects of a pilot barre exercise intervention on balance, strength, functional mobility and quality of life in individuals with mild to moderate PD.

Hypothesis 2a: Barre will improve functional balance, defined as an improved score on the Mini-BESTest.

- MCID- A 4-point increase in total score will denote a clinically-meaningful improvement in functional balance.²⁷

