Hypothesis 2b: Barre will improve functional lower extremity strength, defined as decreased time taken to complete the Five Times Sit to Stand assessment.

Additional functional strength assessments explored include a timed stair ascent and descent task and the Timed Up and Go test.

- MCID- A 2.3 second decrease²⁸ will denote a clinically-meaningful improvement in Five Times Sit to Stand assessment. There are no valid MCIDs for the timed stair ascent and descent task and the Timed Up and Go test. Therefore, a small effect size will be considered a positive effect for each of these tests.

Hypothesis 2c: Barre will improve functional mobility, defined as an improvement average gait speed measured in the Ten Meter Walk Test. Additional gait assessments explored include fast as possible and backwards walking in the Ten Meter Walk Test and distance covered in the Two Minute Walk Test.

- MCID- A 0.05 m/s increase in gait speed will denote a moderate clinically-meaningful improvement in forward, normal gait speed.²⁹ There is no valid MCID for the Two Minute Walk Test. Therefore, a small effect size will be considered a positive effect.

Exploratory Hypothesis 2d: Barre will improve quality of life, as measured by the Parkinson's Disease Questionnaire (PDQ-39).

- MCID- A 4.22-point increase on the PDQ-39 will denote clinically-meaningful improvement in quality of life.³⁰

V. MONITORING

The data safety and monitoring plan includes recording all reportable events according to the IRB policy. The PI will review all reportable events as they occur.

Study progress and safety will be checked monthly for accuracy, compliance, and completeness by the senior scientist and concerns will be discussed with the PI.

References

2. Jankovic J. Parkinson's disease: clinical features and diagnosis. *J Neurol Neurosurg Psychiatry.* 2008;79(4):368-376. doi:10.1136/jnnp.2007.131045

4. K S. Levodopa unresponsive symptoms in Parkinson disease. *Mov Disord Off J Mov Disord Soc.* 2008;23 Suppl 3. doi:10.1002/mds.22049

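### Clinical significance is judged from the bare group mean against an MCID, with no spread, interval or count of participants who reached it

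*Combined protocol and SAP*

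**What the plan says.** The study is a single-arm pilot: "Individuals with PD (N=15) will be recruited to participate in a pilot barre exercise class", and "All participants will be assigned to the pilot barre exercise intervention".

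In section IV (Statistical Analyses), the paragraph before Aim 2 cites the preliminary nature of the study and its small sample, and says that "only motor trends, defined as average group change in score from pre- to post-intervention will be reported". It adds that "published MCIDs will be used to establish if the average improvement of the group reached clinical significance".

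The thresholds follow under each hypothesis. For the Mini-BESTest, "A 4-point increase in total score will denote a clinically-meaningful improvement in functional balance". For sit-to-stand, "A 2.3 second decrease²⁸ will denote a clinically-meaningful improvement in Five Times Sit to Stand assessment". Normal forward gait speed has a threshold of 0.05 m/s and the PDQ-39 one of 4.22 points, which is written as an increase.

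Stairs, the Timed Up and Go and the Two Minute Walk Test are said to have no valid MCID. For these, a small effect size counts as a positive effect, with no value or formula given.

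Nowhere does the plan call for a count of participants reaching an MCID, for individual changes, or for an SD, median or confidence interval of the change. It counts individuals only for feasibility, for example those attending at least 75% of classes.

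**The concern.** An MCID is normally read as a change large enough to matter to a patient. A mean above that value does not show that a typical participant changed by that much, and a mean below it does not show that few did. The mean alone says nothing about how the changes were distributed, and in a group of 15 one or two large changes can carry it across the line.

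The word "only" makes this a stated restriction, not detail left for later. For the four outcomes with an MCID, this rule supplies the clinical interpretation of Aim 2. A reader planning a follow-on trial would see a verdict of clinical significance, or its absence, without the information needed to judge it: how variable the changes were, how precise the mean is, and how many people improved by the stated amount.

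**Working it through.** The documents give no sample-size calculation and no SD of change, so there is no figure of the plan's own to reproduce. The check asks whether the verdict on the mean and the count of participants can disagree at the planned size.

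**Inputs from the documents.** N = 15 (Specific Aims); the four MCIDs (section IV); retention target 75%, so 0.75 × 15 = 11.25, or at least 12 completers.

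**Step 1: constructed examples.** Mean = sum of changes / 15. Count = participants whose own change is at or beyond the MCID. Changes are expressed as improvements.

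| Outcome (MCID) | Changes | Mean | Verdict on mean | Reach MCID |
|---|---|---|---|---|
| Mini-BESTest (4) | 5 × 10, 10 × 1 | 60/15 = 4.0 | reached | 5/15 (33%) |
| Mini-BESTest (4) | 11 × 5, 4 × 0 | 55/15 = 3.67 | missed | 11/15 (73%) |
| Sit to Stand (2.3 s) | 3 × 12, 12 × 0 | 36/15 = 2.4 | reached | 3/15 (20%) |
| Sit to Stand (2.3 s) | 12 × 2.5, 3 × 0 | 30/15 = 2.0 | missed | 12/15 (80%) |
| Gait speed (0.05 m/s) | 5 × 0.16, 10 × 0 | 0.80/15 = 0.053 | reached | 5/15 (33%) |
| Gait speed (0.05 m/s) | 12 × 0.06, 3 × 0 | 0.72/15 = 0.048 | missed | 12/15 (80%) |
| PDQ-39 (4.22) | 5 × 13, 10 × 0 | 65/15 = 4.33 | reached | 5/15 (33%) |
| PDQ-39 (4.22) | 12 × 5, 3 × 0 | 60/15 = 4.0 | missed | 12/15 (80%) |

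Both kinds of disagreement are possible for every outcome with an MCID.

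**Step 2: what an SD and interval would have shown.** The 95% interval is mean ± t × SD/√15, with t = 2.145 on 14 degrees of freedom.
- First Mini-BESTest example: SD = √[(5 × 6² + 10 × 3²)/14] = √(270/14) = 4.39. Interval 4.0 ± 2.43, or 1.6 to 6.4.
- Second: SD = √[(11 × 1.33² + 4 × 3.67²)/14] = 2.29. Interval 3.67 ± 1.27, or 2.4 to 4.9.

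Both intervals contain 4. The plan would nevertheless report opposite verdicts, and neither is firm.

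**Step 3: how often, under assumptions.** Because no SD is given, the simulation assumed a true mean change of 0.5 to 1.25 times the MCID, an SD of 1.0 or 1.5 times the MCID, and normal or skewed (shifted exponential) changes. It compared whether the mean met the MCID with whether more than half of participants did.
- N = 15, normal changes, true mean at the MCID: about 10% of trials have the mean met with under half reaching it, and about 10% the reverse.
- N = 15, skewed changes, true mean at the MCID: about 33% disagree in the direction of the skew, and under 1% in the other.
- All settings, N = 11, 12 and 15: disagreement in a single direction ranges from about 0% to 43%.

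**Step 4: precision of the count.** Exact (Clopper-Pearson) 95% intervals: 5/15, 12% to 62%; 8/15, 27% to 79%; 11/15, 45% to 92%; with 12 completers, 7/12, 28% to 85%. The denominator matters too: 5 people reaching the MCID are 33% of 15 enrolled but 42% of 12 completers.

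**The case against.** The strongest defence is that this is a small pilot whose primary outcomes are feasibility and acceptability. The plan itself calls the motor results trends, and no test, sample size or stated go/no-go decision depends on the MCID verdict. The examples are constructed. With symmetric changes and a true mean at the MCID, half of participants are expected to reach it, so a gross mismatch needs skew, outliers or chance. A percentage at N = 15 is imprecise and dichotomises continuous data. Without a control arm, it also mixes response with measurement error and practice effects. All of this stands, and it limits both the severity and the remedy. It does not rescue the wording, because the bare mean has the same weaknesses and shows none of them.

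Several stronger readings are tempting but not supported.
- *The mean can pass although most participants did not benefit.* In the first Mini-BESTest example all 15 gain something; ten fall short of the MCID. Only the latter can be said.
- *This is the only rule for reading the motor results.* Stairs, the Timed Up and Go and the Two Minute Walk Test use an effect-size rule, and the hypotheses themselves define improvement simply as a better score, time or speed.
- *With normal changes around a mean of 3.5 (assumed SD 2 to 4), 40% to 45% reach 4 points, so a missed verdict is misleading.* That share is below half and agrees with the verdict.
- *A participant who becomes unable to do the sit-to-stand test vanishes from the mean.* The protocol describes the starting position ("Participants will be asked to start sitting with their arms folded across their chest and with their back against the chair") but is silent on inability. What would then happen is inference, and it is a separate missing-data question.
- *The thresholds are valid only for individuals.* How each was derived lies in cited sources that are not available here.

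**Conclusion.** The point holds for the four outcomes with an MCID. The plan declares clinical significance from a group mean alone, and at about 15 participants that verdict can be reached when most people fall short of the MCID, or missed when most attain it. That both can happen is plain arithmetic on the plan's own thresholds. How often they would happen is not known: the figures of about 10% in each direction for normal changes and about 33% for skewed changes, with the true mean at the MCID, rest on assumed distributions.

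Severity is minor to moderate. The affected outcomes are secondary or exploratory, Aim 1 is untouched, and the harm is to what Aim 2 can be said to show. A reader might infer that the share reaching the MCID should replace the mean as the main result. The documents do not support that: the share is less precise, discards information, and in a single arm is no better protected against practice effects.

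**What to change.** For each of the four outcomes with an MCID:
- Keep the mean change as the main summary, with its SD and 95% interval.
- Beside it, give the number and percentage of participants whose own change reaches the MCID, with an exact 95% interval, and the number who worsened by the same amount.
- Show the individual changes in a plot or listing.
- State the denominator (enrolled or completers) and how participants without a post-intervention assessment are counted.

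Replace the claim that the group mean reached clinical significance with a description of where the mean and its interval lie relative to the MCID, together with the count. Before applying the PDQ-39 threshold, settle the scoring direction: the plan writes improvement as an increase and does not say which direction is better.

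The cost is a few sentences in the analysis section and one small table and figure from data already being collected. The downside is that the percentages will look imprecise (5/15: 12% to 62%) and, without a control arm, include measurement error and practice effects. The report should say so.

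### Hypotheses 2a to 2c are defined by direction alone in one uncontrolled group, with no interval planned and no statement of whether direction or the MCID decides them

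*Combined protocol and SAP*

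**What the plan says.** **Hypotheses.** Sections I and IV each give the hypothesis and its definition in one sentence. For balance: "Hypothesis 2a: Barre will improve functional balance, defined as an improved score on the Mini-BESTest". For strength: "Barre will improve functional lower extremity strength, defined as decreased time taken to complete the Five Times Sit to Stand assessment". Hypothesis 2c has the same form, for average gait speed on the Ten Meter Walk Test. Section I attaches no MCID to any of them.

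**MCIDs.** Section IV adds an MCID under each: 4 points on the Mini-BESTest, 2.3 s on Five Times Sit to Stand and 0.05 m/s for comfortable forward gait speed. These are to be used, in addition to the average change, to judge whether the group's mean improvement was clinically significant. For the stair task, Timed Up and Go and Two Minute Walk Test, which Section IV says have no valid MCID, a small effect size counts as a positive effect.

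**Analysis.** Section IV limits the reporting: "Due to the preliminary nature of the study and small expected sample size, only motor trends, defined as average group change in score" from before to after the programme. No SD, interval or test is mentioned.

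**Design.** Section I: "Individuals with PD (N=15) will be recruited to participate in a pilot barre exercise class". Section III, Intervention: "All participants will be assigned to the pilot barre exercise intervention". There is one assessment visit before the programme and one after.

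**Aim 2.** Section I has "Determine preliminary effects of a pilot barre exercise intervention on balance, strength, functional mobility and quality of life". Section IV has "Aim 2: Determine the effects of a pilot barre exercise intervention on balance, strength, functional mobility and quality of life".

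**The concern.** Three things come together.

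- **The criterion is not settled.** The definitions inside 2a to 2c are met by any mean change in the right direction, however small. The MCID lines below them could be a higher grade given to an improvement already declared, or they could be the bar itself. The text supports both readings and chooses neither.
- **Uncertainty is not reported.** A mean change in about 15 people is compared with zero or with an MCID as a bare number. A reader cannot tell a mean that clears the bar comfortably from one that clears it by chance.
- **The wording is causal and the design is not.** With one group and a single baseline test, a gain from taking the test a second time looks the same as a gain from the class.

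At stake is what the pilot report may say about balance, strength and mobility. Followed as written, it could state that barre improved an outcome, or that the improvement was clinically meaningful, from a point estimate alone. It would also leave anyone planning a later study without an SD of change.

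**Working it through.** The plan states no alpha, power, SD or sample-size derivation, so there is no figure of its own to reproduce.

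**Inputs from the documents.** n = 15 (Section I). The retention target in Section IV is "75% of recruited participants will complete the intervention and remain enrolled for the duration of the study": 0.75 × 15 = 11.25, so at least 12 completers. The MCIDs are 4 points, 2.3 s and 0.05 m/s.

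**Assumed inputs.** The documents give neither the SD of change nor the size of any retest gain. Both are assumptions below, shown as ranges. Mean change is treated as normally distributed.

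**1. If direction decides.** Let d be the true mean change divided by the SD of change, in the favourable direction. Then P(favourable mean) = Φ(d√n).

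- No effect and no drift: Φ(0) = 50% per outcome at any n. The Mini-BESTest is scored in whole points, so exact ties are possible. Simulation with rounded changes (SD 2 to 4 points, n = 15) gives 47% to 49%.
- Ineffective class with drift:

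| d (assumed) | n = 15 | n = 12 |
|---|---|---|
| −0.1 (decline) | 35% | 37% |
| 0.1 (retest gain) | 65% | 64% |
| 0.2 | 78% | 76% |
| 0.3 | 88% | 85% |
| 0.5 | 97% | 96% |

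**2. If the MCID decides.** With no true change, P(mean reaches MCID) = 1 − Φ(MCID × √n / SD).

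- Gait speed, SD 0.08 m/s, n = 15: 0.05 × 3.873 / 0.08 = 2.42, giving 0.8%.
- Gait speed, SD 0.20 m/s, n = 15: 0.05 × 3.873 / 0.20 = 0.968, giving 16.7%.
- Gait speed over the same SDs, n = 12: 1.5% to 19.3%.
- Five Times Sit to Stand, SD 3 to 6 s, n = 15: 0.2% to 6.9%.
- Mini-BESTest, SD 2 to 5 points, n = 15: at most 0.1%.

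An assumed retest gain of 0.25 SD subtracts 0.25 × 3.873 = 0.968 from the gait-speed z-values at n = 15. They become 1.45 and 0, so the bar is met 7% to 50% of the time by an ineffective class.

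**3. What an interval would show.** The half-width of a 95% t-interval, in SDs of change, is t(0.975, n − 1)/√n: 0.55 at n = 15 and 0.64 at n = 12. For gait speed at n = 15 that is 0.554 × 0.08 = 0.044 m/s up to 0.554 × 0.20 = 0.111 m/s. An observed mean exactly at the MCID would have an interval of 0.006 to 0.094 m/s in the first case and −0.061 to 0.161 m/s in the second. The planned report would describe both results identically.

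**The case against.** The strongest reply is that this is a pilot that says it will describe trends. Section IV puts that limit directly above Aim 2, lists no test and has no go/no-go rule. Under Outcome Measures, 2a to 2c rest on secondary outcomes behind feasibility and acceptability (although the Ten Meter Walk Test paragraph in Section III calls comfortable gait speed primary). The single-arm design is stated openly. This stands as far as it goes: a reader might infer that the study will formally declare success for an ineffective class half the time, and the documents do not support that. No such declaration is planned, and 50% applies only if direction decides and net drift is zero.

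The second reply also has force. The small-effect-size fallback suggests that, where an MCID exists, the MCID is the bar for a positive effect. On that reading the 50% figure does not apply, and a chance pass is very unlikely for the Mini-BESTest. It remains material for gait speed if the SD of change is large.

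Other tempting readings also fail:

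- **At least one hypothesis met.** With no change, at least one of 2a to 2c has a favourable mean 87.5% of the time if independent (1 − 0.5³), or about 75% at correlation 0.5. The plan makes no such joint claim. Hypothesis 2d does not belong in the count, because it is exploratory and names a measure without defining a direction.
- **A known retest gain.** The documents give no size for one, and they describe the disease as progressive, which pulls the other way.
- **The missing word in the Section IV aim.** This is editorial. The paragraph just above still calls the study preliminary.

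Describing results as trends does not, however, remove definitions that equate any favourable trend with improvement by barre, and it is no reason to omit the SD and interval.

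**Conclusion.** The point holds as one of wording and reporting, and should be corrected. It does not touch the feasibility and acceptability aims. Hypotheses 2a to 2c are worded by direction alone, the role of the MCID in deciding them is unstated, no measure of uncertainty is planned, and causal language is used without a comparison group.

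The size depends on the reading. If direction decides, a favourable mean occurs about 50% of the time per outcome with no effect and no drift. If the MCID decides, the gait-speed bar is met about 1% to 17% of the time with no true change at n = 15, resting on an assumed SD of change of 0.08 to 0.20 m/s. The attribution problem is the same under both readings, because the MCID too is compared with an uncontrolled point estimate.

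**What to change.** In Section IV:

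1. Replace the sentence restricting the report to average group change with: mean within-group change, SD and 95% t-interval for each outcome, with the interval read against both zero and, where there is one, the MCID.
2. State whether direction or the MCID decides Hypotheses 2a to 2c.

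In Sections I and IV, reword the hypotheses and Aim 2 as estimating preliminary within-group change. State that the change will not be attributed to barre because there is no comparison group.

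The interval should not become a rule that allows the word improved only when zero is excluded. That would bring in a significance test the study chose not to run, and it would not cure attribution: an assumed pure retest gain of 0.5 SD would still pass 43.8% of the time at n = 15. The statement on attribution deals with that limit in the report; only a control group or repeated baseline would resolve it in the design.

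No new visits, participants or data are needed. The cost is less favourable efficacy statements, since at n = 15 the interval extends about 0.55 SD of change on either side of the mean.

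### The PDQ-39 threshold has the wrong sign: a 4.22-point increase is labelled an improvement, although on standard scoring a higher PDQ-39 score means worse quality of life

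*Combined protocol and SAP*

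**What the plan says.** Section IV (Statistical Analyses) judges the Aim 2 outcomes by comparing the group's mean change with a threshold taken from the literature: "published MCIDs will be used to establish if the average improvement of the group reached clinical significance". For motor outcomes it defines the summary as "only motor trends, defined as average group change in score from pre- to post-intervention will be reported". Read in that order, an increase is a post-intervention score above the pre-intervention score.

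Under Exploratory Hypothesis 2d, which predicts better quality of life, the criterion is: "A 4.22-point increase on the PDQ-39 will denote clinically-meaningful improvement in quality of life". The figure is referenced to source 30.

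The Outcome Measures list describes the instrument only as "a patient-reported questionnaire that assesses PD-specific health quality of life in the past month". The PDQ-39 is also mentioned under Specific Aims and in the descriptions of the two visits. None of these places gives a score range, says which end of the scale is favourable, or mentions recoding.

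**The concern.** The PDQ-39 records how often Parkinson-related problems occurred, and in its standard form a higher score is worse. A gain in quality of life is therefore a fall in the score, and the plan asks for a rise.

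This sentence is the only numerical criterion for quality of life, which is named in the primary objectives and in Aim 2. The study has a single group, and no significance test is described for the Aim 2 outcomes. The comparison with the published threshold is therefore all the plan offers by way of interpretation, and no later analysis step would expose a reversed sign. An analyst who follows the text could report harm as benefit. One who notices the slip has to depart from the written plan without a documented reason.

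**Working it through.** The plan derives no figure here that could be reproduced: 4.22 is taken from a cited source, and no SD, alpha or power is given. The check is one of direction, followed by an illustration of size.

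**Step 1. Compare the thresholds within Section IV.**

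| Outcome | Favourable direction | Direction in the plan | Consistent? |
|---|---|---|---|
| Mini-BESTest | higher | +4 points | yes |
| Five Times Sit to Stand | lower (time) | −2.3 s | yes |
| Forward gait speed, 10MWT | higher | +0.05 m/s | yes |
| PDQ-39 | lower (standard scoring) | +4.22 points | **no** |

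For balance the text reads "A 4-point increase in total score will denote a clinically-meaningful improvement in functional balance". For the sit-to-stand test, a 2.3 second decrease "will denote a clinically-meaningful improvement in Five Times Sit to Stand assessment". The section therefore writes each threshold on the raw scale and uses a decrease where lower is better. It does not follow a convention in which an increase stands for improvement on every measure. Only the PDQ-39 entry fails to fit.

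**Step 2. Compare the decision regions.** Let D be the mean change, post minus pre.

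- Written rule: improvement if D ≥ +4.22.
- Corrected sign, same magnitude: improvement if D ≤ −4.22.

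The regions do not overlap. For D between −4.22 and +4.22 both rules say the threshold was not reached. Beyond 4.22 points in either direction they give opposite answers. This holds for any SD and any sample size.

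**Step 3. Illustrate the size.**

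Inputs: n = 15 (Specific Aims); threshold 4.22 (Section IV). The SD of change is not in the document and is assumed to be 8, with a range of 6 to 12. The true mean change μ is set at 5 points in either direction, also an assumption.

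Formulas (normal approximation), with SE = SD/√n:

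- P(written rule declares improvement) = 1 − Φ((4.22 − μ)/SE)
- P(corrected rule declares improvement) = Φ((−4.22 − μ)/SE)

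At SD = 8, SE = 8/√15 = 2.066.

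- True improvement, μ = −5, written rule: (4.22 + 5)/2.066 = 4.46, so the probability is below 0.0001.
- True improvement, μ = −5, corrected rule: (−4.22 + 5)/2.066 = 0.378, so Φ = 0.647.
- True worsening, μ = +5, written rule: (4.22 − 5)/2.066 = −0.378, so 1 − Φ = 0.647.

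| Assumed SD | Written rule, true worsening of 5 | Corrected rule, true improvement of 5 | Written rule, true improvement of 5 |
|---|---|---|---|
| 6 | 0.693 | 0.693 | <0.0001 |
| 8 | 0.647 | 0.647 | <0.0001 |
| 10 | 0.619 | 0.619 | 0.0002 |
| 12 | 0.599 | 0.599 | 0.0015 |

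**Step 4. Vary the true change and the number of completers.**

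- If the true change equals the threshold (μ = ±4.22, n = 15), the rule pointing in the direction of the change is met with probability 0.50. The opposite rule is met with probability below 0.0001, 0.0001 and 0.003 at SD 6, 9 and 12.
- At the plan's 75% retention target, 0.75 × 15 = 11.25, or 12 completers. With SD 8, SE = 8/√12 = 2.309 and 0.78/2.309 = 0.338, so 0.647 becomes 0.63.
- With no true change (n = 15), both rules are met equally often: 0.003, 0.035 and 0.087 at SD 6, 9 and 12. The wrong sign matters only when quality of life really changes.

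**The case against.** The strongest objection concerns the premise. The document never states that a higher PDQ-39 score is worse; that comes from general knowledge of the instrument. This is true and should be stated openly. It is, however, the basic scoring of a named, standard questionnaire and not a figure recalled from a cited paper. The sentence would be right only if the score were reversed or the change taken as pre minus post, and the plan says neither. Even without the premise, the plan sets a directional criterion on a scale whose direction it does not define.

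A second objection is that the threshold does not strictly decide Hypothesis 2d. The hypothesis contains no number, and the general sentence on thresholds presupposes that the group has improved before asking whether the improvement is large enough. An analyst who uses the scoring manual might catch the slip. This stands in part: a false report could follow from the text but is not inevitable. The plan also speaks of reporting only motor trends, so it is unclear how the PDQ-39 result will be reported at all.

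Third, the reach is limited. The PDQ-39 is exploratory and listed among the additional outcomes. Participation, retention and satisfaction, the sample size and the safety monitoring do not depend on it. This stands in full.

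Finally, the probabilities rest on an assumed SD and an assumed true change. They do, and they only give a sense of scale. The reversal in Step 2 needs neither.

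**Conclusion.** The concern holds. On standard PDQ-39 scoring the criterion is reversed: it gives the opposite conclusion for any group mean change of 4.22 points or more in either direction. With 15 participants, an assumed SD of 6 to 12 and a true worsening of 5 points, the written rule declares clinically meaningful improvement with probability 0.69 to 0.60. For a true 5-point improvement it does so with probability of at most about 0.0015.

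The conclusion rests on two assumptions: that the score is used in its standard direction, which nothing in the document contradicts, and that the rule is applied as written. The damage is confined to one exploratory outcome. Within that outcome, though, the rule is wrong as written and should be corrected before the PDQ-39 data are analysed. Whether 4.22 is the right magnitude for an improvement cannot be settled from the document.

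**What to change.** In Section IV, under Exploratory Hypothesis 2d:

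1. Replace *increase* with *decrease*.
2. Add a clause stating that the PDQ-39 summary index runs from 0 to 100 with higher scores worse, and that change is post minus pre. If the team intends to use a reversed score, say so explicitly and keep *increase*.
3. Check in reference 30 that 4.22 is the threshold for improvement and not for worsening. If the two differ, correct the number together with the direction.
4. State whether the PDQ-39 mean change will be reported, since the present wording covers only motor trends.

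The cost is one word, one or two clauses and a look at a source already cited. Data collection and sample size do not change. The correction should be dated and, if possible, made before anyone sees the post-intervention PDQ-39 scores, so that it cannot be read as a response to the result.
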